2. Determine the approximate frequency of each independently studied imaging biomarker to facilitate power calculations.
3. Determine if FDG PET activity and MR biomarkers are highly correlated and thus potential surrogates, or if these are discrepant and possibly complementary.
4. Perform an exploratory evaluation of DWI for assessment of facet joints.
5. Assess the concordance of findings on gadolinium enhanced MRI with T2 fat-suppressed MRI using both axial and sagittal images to determine if gadolinium administration will be necessary for future clinical investigation.

We plan to screen up to 40 patients to ensure we enroll 10 subjects.

3. Hypothesis/Study Category:

This is an exploratory study investigating the utility of FDG PET activity and MRI signal change around facet joints in the clinical management of low back pain. This study will help determine if such imaging biomarkers could change clinical management. Additionally, this will provide data that will be vital to planning a larger prospective study evaluating the ability of imaging biomarkers to predict response to comparison medial branch blocks and RF ablation for treatment of facet joint pain. Such a prospective study could not be adequately designed without this initial exploratory component.

4. Methodology

4.1. Patient Enrollment

Eligibility criteria - inclusion:

1. Male and female patients over the age of 50-100 years with clinically suspected facetogenic low back pain.
2. Patients must be considered to have at least a 60% chance of having facet joints as the major source of low back pain based on overall clinical impression.
3. All patients will undergo a standardized clinical exam by an experienced physical medicine and rehabilitation clinician to confirm clinical suspicion of axial low back pain.
4. Patients with either unilateral or bilateral axial low back pain may be enrolled.

Eligibility criteria - exclusion:

1. Pregnancy
2. Prior lumbar back surgery
3. History of endovascular repair of abdominal aortic aneurysm or other postoperative change likely to introduce imaging artifact to the lumbar spine
4. Suspected spine infection
5. Known osseous metastatic or other osseous malignancy
6. Facet joint percutaneous treatment within the past 2 months
7. History of major lumbar spine trauma
8. Inability to provide own consent
9. Claustrophobia, cardiac pacemaker/wires in place, any absolute contraindication to MRI
10. Impaired renal function indicated by a GFR less than 30
11. Gadolinium allergy
12. Highly radiosensitive medical conditions
13. Patients who are unable to lay quietly for 60 minutes of imaging

4.2 Patient Preparation

A Review Preparatory to Research will be conducted by the study coordinators to determine if the patient meets inclusion criteria including a pre-screen for MRI safety and body habitus and whether the patient's schedule will allow for study participation.

4.3 Patient Scanning Protocol

The PET/MR study consists of an injection of 12 mCi (+/-10%) fluorodeoxyglucose (FDG) and an uptake period of 60 minutes followed by a PET/MRI on the Signa PET/MR system. Patients will need to fast for 18 hours prior to the injection. The patients may require a creatinine check per routine MRI clinical protocol. Patients may request sedation to make the scan more comfortable. They will be given Ativan by mouth to relax by the MR/PET nurse. As per Radiology Departmental policy, the additional MR images obtained during the study will also be given a full clinical read by the staff radiologists to ensure no unexpected findings.

Patients will undergo one scan for this study.

MRI Sequences

1. Sagittal and axial T2 images with fat saturation Lumbar spine
2. Sagittal and axial T1 images with gadolinium and fat saturation lumbar spine
3. A T1 series without fat saturation (volumetric) lumbar spine
4. Axial DWI images lumbar spine

PET images

1. 18F-FDG PET images of the lumbar spine, reformatted in axial and sagittal planes

4.4 Dosimetry

Each patient will receive 12 mCi (+/-10%) F18 FDG

5. Initial Clinical Assessment

1. Patients will undergo a standardized clinical exam by [name], [name] or [name] from the physical medicine rehabilitation department.
2. The clinician will score the likelihood of the lumbar facet joint(s) as a structural source of pain in each patient using a standardized checklist of clinical and physical exam features and overall clinical impression. The patient must have at least 1 clinical and 1 physical exam feature consistent with facet joint pain.
3. The clinician will qualitatively score his/her confidence that the axial low back pain is derived from facet joints using a percentile (i.e. 60-100%).
4. Determination of the likelihood of facet joint pain on the basis of results from prior imaging with fat saturated sequences will not be permitted to avoid selection bias. However, it is not practical to keep clinicians blinded from prior clinical imaging tests.
5. Indicate the treatment plan (including specific facet joints to be treated percutaneously by either steroid injection or medial branch blocks/radiofrequency ablation).
6. The severity (0-10 scale) and duration of pain (months) on each side will be recorded.
7. Patients will undergo the PET/MR examination as soon as both patient and scanner availability allows; the imaging study must be within 3 months of this clinical assessment.

6. Image Analysis

Lumbar facet joint levels (e.g. L4/L5) will be enumerated by the PI prior to scoring for consistency.

MRI Images

1. Two readers will view images independently. The MRI readers will be blinded to the PET images/results.
2. Peri-facet signal change for every lumbar facet joint on MRI will be determined by 2 neuroradiologists using an established 0-4 grading scale for T2 fat-suppressed images first (blinded to the gadolinium enhanced images).
3. Peri-facet signal change for every lumbar facet joint on MRI will be determined by 2 neuroradiologists using an established 0-4 grading scale for gadolinium enhanced T1 fat-suppressed images.
4. Dichotomous qualitative assessment of presence of pure synovial enhancement will be scored separately.

5. Dichotomous qualitative assessment of facet joint effusion will be scored separately.
6. DWI/ADC images will be examined as an exploratory component, each joint rated as normal, increased DWI signal, or true restricted diffusion by visual inspection.
7. After each group of up to 5 studies (or fewer), the 2 readers will re-review the studies together to establish consensus and document reasons for interobserver variability.
8. The consensus facet joint scores will then be grouped into 3 categories for comparison to PET data and clinical translation: 1 = normal (0/4), 2= mild peri-facet signal change (1-2/4), 3 = high grade peri-facet signal change (3-4/4).
9. After each group of 5 studies, the 2 readers will re-review the studies together to establish consensus and identify/document reasons for interobserver variability (if any).
10. The overall score for each lumbar facet joint (L1/L2 through L5/S1) will represent the highest of the 2 consensus grades (of T2 fatsat and T1 fatsat with gad).

PET Images

1. Patients will receive a routine clinical dose of F18 FDG and undergo PET imaging at a standard recorded interval.
2. Every lumbar facet joint will be rated as either normal or having increased activity on qualitative visual inspection independently by 2 nuclear medicine physicians on a scale of normal, mildly increased, or markedly increased (high grade).
3. Maximum standard uptake value (SUV-max) will also be determined and will be compared to the SUV-max of the adjacent normal vertebral body (avoiding areas increased in association with degenerative disc disease).
4. The PET readers can view anatomic T1 images for coregistration, but will be blinded to the fat-suppressed MR images/results.
5. After each group of up to 5 studies (or fewer), the 2 readers will re-review the studies together to establish consensus and identify/document reasons for interobserver variability (if any).
6. The consensus rating by visual inspection will establish the qualitative score.

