6.2 Primary Data Analysis

1. The concordance of qualitative scores of FDG activity with clinical impression will be determined (high grade and all grades).
2. The concordance of overall scores of MR findings with clinical impression will be determined (high grade and all grades).
3. The frequency with which the qualitative scores of FDG activity altered clinical management will be scored (high grade and all grades).
4. The frequency with which the overall scores of MR findings altered clinical management will be scored (high grade and all grades).
5. For each patient, the number (and level) of facet joints prescribed percutaneous treatment will be determined in these 3 categories:
 - a. Number of facet joints with unchanged treatment recommendation
 - b. Number of new facet joints that would be treated with PET/MR data
 - c. Number of facet joints initially prescribed treatment based on clinical exam that would not undergo percutaneous treatment with PET/MR data.
6. The degree of concordance of FDG PET activity and MRI findings will be scored.
7. The frequency of upgrading the overall score with gadolinium images versus T2 images alone will be determined.
8. The frequency of pure facet joint synovial enhancement or effusion without peri-facet signal change will be determined.

9. Qualitative FDG PET scores will be compared to SUV-max scores (absolute and as a ratio to normal vertebral body activity) to determine if quantitative thresholds can be established for future investigation.
10. The concordance of DWI results with other imaging findings and clinical data will be assessed for exploratory purposes.
11. Interobserver variability for both FDG PET scores and MRI scores will be examined.

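### The gadolinium read has no stated blind to T2, so the T2-gadolinium concordance in Aim 5 may partly reflect anchoring

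*Combined protocol and SAP*

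**What the plan says.** All the reading rules are in section 6 (Image Analysis), under MRI Images.

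- **Item 1:** "Two readers will view images independently. The MRI readers will be blinded to the PET images/results". PET is the only thing to which the MRI readers as a group are blinded.
- **Item 2:** two neuroradiologists grade every lumbar facet joint "using an established 0-4 grading scale for T2 fat-suppressed images first (blinded to the gadolinium enhanced images").
- **Item 3:** two neuroradiologists grade the same joints "using an established 0-4 grading scale for gadolinium enhanced T1 fat-suppressed images". The item has no order and no blinding clause.
- **Item 6:** "DWI/ADC images will be examined as an exploratory component, each joint rated as normal, increased DWI signal, or true restricted diffusion by visual inspection". The item gives no reader, order or blind.
- **Items 7 and 9:** after each group of up to five studies, "the 2 readers will re-review the studies together to establish consensus and document reasons for interobserver variability". Neither item says which series are open at that meeting.
- **Item 10:** the overall score for a joint "will represent the highest of the 2 consensus grades (of T2 fatsat and T1 fatsat with gad").

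Three parts of the plan use these grades. Aim 5 assesses T2-gadolinium concordance "to determine if gadolinium administration will be necessary for future clinical investigation". Section 6.2 item 7 counts how often gadolinium raises the overall score above T2 alone. Section 6.2 item 10 covers diffusion imaging: "The concordance of DWI results with other imaging findings and clinical data will be assessed for exploratory purposes".

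**The concern.** Concordance between two gradings is easiest to interpret when the second is made without knowledge of the first. Here the protection runs one way. The T2 grade is shielded from gadolinium, but nothing shields the gadolinium grade from T2. If the same reader grades the same joint on the same 0-4 scale, a remembered or visible T2 grade can pull the gadolinium grade towards it. The plan accepts the principle elsewhere, since MRI readers are blinded to PET and PET readers to the fat-suppressed MRI.

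At stake is the answer to Aim 5. Agreement raised by anchoring would make gadolinium look less necessary than independent reads would show, and this study is meant to supply the design of a larger prospective one.

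**Working it through.** The documents give no expected agreement, kappa or upgrade frequency, so there is no planned figure to reproduce. The check compares the reading rules with the analyses, then illustrates the size on assumed values.

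**1. Which blinds exist**

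| Read | Stated blind to the other MRI series | Reader stated |
|---|---|---|
| T2 fat-suppressed (item 2) | Yes, to gadolinium | Two neuroradiologists |
| Gadolinium T1 (item 3) | None | Two neuroradiologists |
| DWI/ADC (item 6) | None | Not stated in the item |
| Consensus re-review (items 7, 9) | None | The two readers |

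That one pair reads both T2 and gadolinium is the natural reading of items 1, 7 and 9, though it is not stated item by item. No separate session, reshuffled order or locking of grades appears anywhere in the document.

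**2. What each analysis needs**

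Let T be the T2 consensus grade and G the gadolinium consensus grade. By item 10 the overall score is max(T, G), so the upgrade counted in section 6.2 item 7 is max(T, G) - T = max(0, G - T).

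- For this add-on quantity, the contamination to prevent is gadolinium information entering T. Item 2 prevents it at the individual read. The consensus step does not, because no blind is stated there. If T is settled with gadolinium in view and drifts towards G, the upgrade shrinks.
- For concordance as an agreement measure (Aim 5), G should also be graded without knowledge of T. No rule provides for that.

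**3. Illustrative size of anchoring**

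Assume unblinded readers repeat the T2 grade on a fraction p of the joints they would otherwise have graded differently. With independent-read agreement A and upgrade frequency u:

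- observed agreement = A + (1 - A)p
- observed upgrade frequency = u(1 - p)

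With assumed A = 0.70 and u = 0.15:

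| p | Observed agreement | Observed upgrades |
|---|---|---|
| 0 | 70% | 15% |
| 0.25 | 0.70 + 0.30 × 0.25 = 77.5% | 0.15 × 0.75 = 11.25% |
| 0.50 | 0.70 + 0.30 × 0.50 = 85% | 0.15 × 0.50 = 7.5% |

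On the kappa scale with equal marginals, observed kappa = k + a(1 - k), where a is the probability of repeating the T2 grade. For an assumed k = 0.60, a = 0.10, 0.25 and 0.50 give 0.64, 0.70 and 0.80. A simulation with three categories (assumed marginals 0.5, 0.3, 0.2) gave 0.641, 0.700 and 0.801.

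**4. Precision and reread noise**

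Ten subjects with five levels on two sides give 10 × 5 × 2 = 100 joints. An upgrade count of 15/100 has a 95% Wilson interval of about 9% to 23%, ignoring clustering within patients. The illustrated 11.25% lies inside that interval and 7.5% just below it.

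The same example leaves 100% - 70% - 15% = 15% of joints graded lower on gadolinium. Equal upward and downward disagreement is what pure rereading noise would produce with no real gain from gadolinium. The 15% therefore cannot be taken as the true benefit.

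**The case against.** The strongest reply is that the one-way blind suits the analysis the plan specifies. Section 6.2 item 7 starts from T2 and asks whether gadolinium raises the score, and item 2 blocks the leak that would spoil that comparison at the individual read. A fully independent reread has its own bias: under a highest-of-two rule, every upward reading error counts as an upgrade. Both arguments stand. A reader might infer that item 7 is biased by design; the documents do not support that. What the reply leaves open is the concordance named in Aim 5 and the unblinded consensus step.

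Three other strong readings also go too far.

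- **That the bias must favour dropping gadolinium.** Anchoring towards agreement is the likely direction, but a reader looking for added findings could upgrade more often.
- **That DWI is rated afterwards by the same readers, so its concordance is inflated.** Item 6 states neither reader nor order, the DWI categories are not the 0-4 scale, and the component is labelled exploratory. The documents show only that reader, order and blind are unspecified.
- **That the gadolinium grade is given straight after the T2 grade.** T2 comes first, but the plan states no interval between the reads.

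**Conclusion.** The concern holds in limited form. As written, the gadolinium grade need not be independent of the T2 grade, so Aim 5 concordance can be affected by anchoring, most likely upwards. The T2 consensus grade is also unprotected from gadolinium at the joint re-review, and that does touch the add-on analysis in section 6.2 item 7.

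The size is unknown and cannot be estimated from the planned data, because no gadolinium read blinded to T2 is planned. The 70%, 15% and 25% to 50% inputs, like the kappa and a values, are assumptions that show the mechanism; a reader should not take them as predictions. The conclusion also assumes that the same two readers grade both series.

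This is a cheap improvement to an exploratory study of 10 patients, best made before reading starts. It does not undermine the rest of the plan.

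**What to change.** 1. **Amend MRI item 3.** Have the same two readers grade the gadolinium series in a separate session, with case order reshuffled and T2 images and grades hidden. Lock each reader's grades.
2. **Aim 5.** Report T2-gadolinium concordance per reader from the locked grades, so that no rule for combining readers is needed. Show upward and downward disagreements separately, so that rereading noise is visible.
3. **Amend MRI items 7 and 9.** Lock the T2 consensus grade before the gadolinium series is opened at the consensus meeting.
4. **Section 6.2 item 7.** Compute it as the change from the locked T2 consensus grade to the overall consensus score, and describe it as add-on value.
5. **Overall score.** Leave its definition as it is for section 6.1.
6. **DWI (item 6).** State the reader, order and blind. Rating DWI before the T2 and gadolinium grades, or with them hidden, is a minor exploratory addition.

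The cost is one extra reading session for 10 patients (100 joints per reader) and some protocol wording. The downside is that a gadolinium read without T2 alongside differs from clinical reading; the consensus meeting still supplies the combined read. Sample size and scanning do not change.

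### The blinding of T2 to gadolinium is stated for the first read only, not for the consensus T2 grade on which the gadolinium upgrade rate appears to rest

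*Combined protocol and SAP*

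**What the plan says.** Aim 5 (Section 2) compares gadolinium-enhanced with T2 fat-suppressed MRI "to determine if gadolinium administration will be necessary for future clinical investigation". The matching analysis is Section 6.2 item 7: "The frequency of upgrading the overall score with gadolinium images versus T2 images alone will be determined".

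The grades come from the MRI list in Section 6, Image Analysis:

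- Item 1, first reads: "Two readers will view images independently. The MRI readers will be blinded to the PET images/results".
- Item 2, T2: two neuroradiologists use a 0-4 "grading scale for T2 fat-suppressed images first (blinded to the gadolinium enhanced images").
- Item 3, gadolinium: they use a 0-4 "grading scale for gadolinium enhanced T1 fat-suppressed images".
- Item 7, consensus: "After each group of up to 5 studies (or fewer), the 2 readers will re-review the studies together to establish consensus". Item 9 repeats this almost word for word. Neither item names a series.
- Item 10, overall score per joint: it "will represent the highest of the 2 consensus grades (of T2 fatsat and T1 fatsat with gad").

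Section 6.2 item 11 also examines interobserver variability, so the individual grades have to be kept.

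**The concern.** Item 2 shows that the authors foresaw carry-over from gadolinium to T2 and guarded against it. The guard is stated for the individual read only. The grades that enter the overall score are consensus grades, and consensus is set by the two people who, in the listed order, have by then graded enhancement in the same joints. Nothing says that the T2 consensus is settled first, or with the gadolinium images closed.

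Where the readers split on T2, what they saw on gadolinium can decide the T2 grade. The comparator in Section 6.2 item 7 would then no longer reflect T2 by itself, and the two series would look more alike than independent grading would show. The result bears directly on whether gadolinium is kept in the larger study. Disagreement is to be expected: the introduction cites the team's own unpublished data as showing that imaging parameters with low interobserver variability still have to be developed.

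**Working it through.** **No figure to reproduce.** The documents give no expected upgrade rate, reader error rate or decision threshold. The check is therefore the reading order, then an illustration.

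**Step 1: what counts as an upgrade.** Let T and G be the T2 and gadolinium consensus grades of a joint. By item 10 the overall score is max(T, G). It exceeds T exactly when G > T. The upgrade rate is the share of joints with G > T.

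**Step 2: how consensus can change the count.** Suppose the blinded T2 reads are 1 and 2.
- If G = 2, settling T2 at 1 gives an upgrade and settling it at 2 gives none. Knowledge of G can decide the outcome.
- If G = 3, the joint is an upgrade either way.

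So carry-over acts on some disputed joints, not on all.

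**Step 3: illustration (every input assumed).** 400,000 simulated joints. True T2 grades 0 to 4 have probabilities 0.50, 0.20, 0.15, 0.10 and 0.05. Gadolinium adds one grade with probability g. Each read is off by one grade with probability e, half in each direction, truncated to 0-4. Disagreements are settled by picking one of the two grades at random. Carry-over is a pull of 0.25, 0.5 or 1. In disputed joints it is the probability of choosing the T2 read nearer to G; if all joints are reopened, it is the probability of setting T equal to G.

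Upgrade rates at e = 0.20:

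| g | True | T2 locked | Pull on disputed joints only (0.25 / 0.5 / 1) | Pull on all joints (0.25 / 0.5 / 1) |
|---|---|---|---|---|
| 0 | 0% | 12.7% | 11.6 / 10.6 / 8.5% | 9.5 / 6.3 / 0% |
| 0.10 | 9.5% | 19.2% | 18.1 / 16.9 / 14.7% | 14.4 / 9.6 / 0% |
| 0.20 | 18.9% | 25.7% | 24.5 / 23.3 / 20.8% | 19.3 / 12.9 / 0% |

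Checks by hand:
- True rate at g = 0.10: grade 4 cannot rise, so 0.10 x 0.95 = 9.5%.
- Pull on all joints at g = 0.10: 19.2% x (1 - pull) = 14.4%, 9.6% and 0%.
- Locked rate at g = 0, e = 0.20: for grades 1 to 3, 0.1 x 0.9 + 0.8 x 0.1 = 0.17; for grades 0 and 4, 0.9 x 0.1 = 0.09. Weighted, 0.45 x 0.17 + 0.55 x 0.09 = 12.6%, against 12.7% simulated.

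**Step 4: what the table shows.** Pull towards gadolinium lowers the rate relative to a locked T2 consensus in every row. The locked rate itself lies above the truth, because a low T2 read or a high gadolinium read counts as an upgrade. With no gadolinium effect it is 6.7%, 12.7% and 17.4% for e = 0.10, 0.20 and 0.30. At g = 0.10, the rate with carry-over in disputed joints only (14.7-18.1%) is still above the true 9.5%; with all joints reopened it runs from 14.4% down to 0%.

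**Step 5: sampling error for scale.** 10 subjects x 5 levels x 2 sides = 100 joints (both sides inferred). Ten upgrades in 100 have an exact 95% interval of 4.9% to 17.6%, before allowing for clustering within patients.

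**The case against.** The strongest reply is that the plan is silent rather than wrong. No sentence says that T2 consensus is set with gadolinium in view. Items 7 and 9 are two consensus steps that precede a rule using two consensus grades, so one session per series could be meant. Section 6.2 item 7 does not say that its T2 comparator is the consensus grade, and the blinded first reads could be used instead. Joints on which both readers agreed may never be reopened.

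Much of this stands. A reader might infer that the blinding is certainly broken; the documents do not establish that, because the order within the consensus session is not given. It does not remove the gap, though. Neither item 7 nor item 9 names a series, both are listed after the gadolinium read, and item 8 already uses consensus scores between them. The first reads give two T2 grades per joint, and consensus is the plan's only rule for reducing them to one. If the first reads were meant, the plan needs to say so.

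A second reply is that the bias has no settled net sign, since reading error pushes the rate up. That is correct, and it limits the claim. It is not a defence: an uncontrolled offset between two errors makes the rate harder to interpret.

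A third is that 10 subjects in an exploratory study leave sampling error as large as the distortion in the milder scenarios. That is fair. The consequence falls on a later design decision, not on a test.

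**Conclusion.** The concern holds as a gap in the plan: blinding to gadolinium is stated for the individual T2 read and is not preserved at consensus. Two inferences carry it: that consensus follows both reads, as listed, and that the T2 comparator in Section 6.2 item 7 is the consensus grade. Both are the natural reading; neither is stated.

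The likely effect is a lower upgrade rate than a locked T2 consensus would give. The documents supply no input for its size, so the simulated figures show mechanism and plausible range only.

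Three stronger conclusions are tempting and not supported:
- That the reported rate is biased towards zero. Against the truth the net direction is undetermined.
- That a particular shrinkage can be quoted. It would rest wholly on assumed shares of disputed joints and assumed reader behaviour.
- That the diffusion-weighted ratings are contaminated in the same way. The plan does not state when these are read relative to the other series, and item numbering is not a reading order.

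The change is worth making because it protects the one comparison that serves Aim 5 and costs little.

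**What to change.** 1. In the Section 6 MRI list, for each group of studies: both readers grade T2, hold the T2 consensus and lock it. Only then do they open the gadolinium series, grade it and set its consensus.
2. In Section 6.2 item 7, compute the upgrade rate from the locked T2 consensus and state that this is the T2-alone grade.
3. Reconcile items 7 and 9: merge them, or say which series each covers.
4. Report the number of joints graded higher on T2 than on gadolinium beside the number of upgrades. Locking does not remove upgrades caused by reading error, and the opposite count helps to judge how many there are.
5. For studies already read, also report the comparison from the two readers' blinded pre-consensus T2 grades.

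The cost is protocol wording and the splitting of each consensus meeting into a T2 part and a gadolinium part. No extra patients, scans or readers are needed.
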